7.4 Withdrawal of individual subjects

Subjects can leave the study at any time for any reason if they wish to do so without any consequences. The investigator can decide to withdraw a subject from the study for urgent medical reasons.

7.4.1 Specific criteria for withdrawal (if applicable)

Not applicable

7.5 Replacement of individual subjects after withdrawal

If participants drop out of the study before completing the pre-test, they will be replaced by participants fulfilling the inclusion criteria.

7.6 Follow-up of subjects withdrawn from treatment

Not applicable

7.7 Premature termination of the study

< Please describe the criteria for terminating the study prematurely and the procedures in case the study will be terminated prematurely.>
Not applicable

Version number: 5, 06-02-2018

8. SAFETY REPORTING

8.1 Temporary halt for reasons of subject safety

In accordance to section 10, subsection 4, of the WMO, the sponsor will suspend the study if there is sufficient ground that continuation of the study will jeopardise subject health or safety. The sponsor will notify the accredited METC without undue delay of a temporary halt including the reason for such an action. The study will be suspended pending a further positive decision by the accredited METC. The investigator will take care that all subjects are kept informed.

8.2 AEs, SAEs and SUSARs

8.2.1 Adverse events (AEs)

Adverse events are defined as any undesirable experience occurring to a subject during the study, whether or not considered related to [the investigational product / trial procedure/ the experimental intervention]. All adverse events reported spontaneously by the subject or observed by the investigator or his staff will be recorded.

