4.2 Inclusion criteria

In order to be eligible to participate in this study, a subject must meet all of the following criteria:

- · Fathers having their first baby.
- The parents must have had the 20-week medical ultrasound via regular health care services.
- Partners of the fathers must be low-risk expecting women with uncomplicated singleton pregnancies between the 21th and 30th week of gestation.

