5. TREATMENT OF SUBJECTS

5.1 Investigational product/treatment

The experimental group (half of the sample, randomly selected) will receive an intervention, the Video-feedback Intervention to promote Positive Parenting – Prenatal (VIPP-PRE; Juffer et al., 2008). This intervention focuses on enhancing parenting sensitivity. Studies using the VIPP intervention have repeatedly been approved by the CCMO (document nr: NL49069.000.14 and NL50277.058.14). The VIPP is the only parenting intervention which is indicated as established effective in the Database of Effective Youth Intervention from the Netherlands Youth Institute (see www.nji.nl). VIPP studies have almost all focused exclusively on mothers and have paid little attention to the role of fathers. One notable exception is the study of Lawrence et al. (2012), showing that the VIPP is suitable for use with fathers and that no specific changes to the intervention are needed. For the current study the VIPP method has been adapted for prenatal use, with ultrasound instead of regular video fragments.

Content of the intervention

The VIPP-PRE consists of three sessions between the 21st and 30th week of pregnancy. Each session lasts for approximately one hour and the sessions take place every 1-2 weeks. Fathers will be invited to interact with the fetus both verbally and by touching and softly massaging the infant through the mother's abdominal wall. For a more detailed description of the intervention see Document F21. This description has previously been approved by the Toetsingscommisie Ethiek Pedagogische Wetenschappen under project number ECPW2017-170. Fathers will be asked to 'communicate' with their unborn babies, made visible through ultrasound. Their partners are thus asked to cooperate and have the ultrasound made. During each session, the first minutes of the ultrasound will be shared with both parents, taking into account the mothers' wish to see her baby as well. The baby's behavior will be made visible through ultrasound.

Control condition

Fathers in the control group will receive telephone calls from a research assistant during the same period and with the same frequency (dummy intervention). During these telephone calls, fathers will be asked about the development of the pregnancy.

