The quality of care (sensitivity) will be observed during parent-child interaction (free play). Secondly, the Five Minute Speech Sample (FMSS) will be used to assess fathers' Expressed Emotions as an index for a sensitive parenting attitude. In the FMSS, parents are asked to describe their child and their relationship with their child. Thirdly, sensitivity will be observed during when fathers are asked to take care of a life-like doll for 10-min (Leiden Infant Simulator Sensitivity Assessment (LISSA); see Bakermans-Kranenburg et al., 2015). Moreover, a brief observation of father-infant interaction (father with his own infant) will be made.

Protection (only during follow-up session)

The Auditory Startling Task (AST) will be used to observe parental protective behavior. The procedure has been used in other labs as well (Herzliya university Tel Aviv, with prof. [name]) with infants and their parents. While the participant plays with the baby, a short sound fragment will be heard. The sound consists of white noise (80-db) and is programmed for 10 seconds with short breaks. This sound is loud enough to elicit a response from the baby, without harming the infant's hearing. At the end of the sound fragment, the research assistant enters the room and apologizes for the sound: "I am so sorry; we had some technical problems and took me a moment to get things under control. Sorry. So, let's move on...". The participant is debriefed about

[figure not shown]
the purpose of the sound fragment at the end of the session. Secondly, protection will be assessed with partner report, using a questionnaire on the extent to which fathers are avoiding and discouraging risk behavior (e.g. hygiene, protection of child from sickness and accidents in the prenatal and postnatal period).

Partners will be asked to accompany the fathers to the LUMC for the follow up session to provide care for the infant when the father is undergoing neural assessments. In the unlikely event the partner is not able to accompany the father and infant, we will arrange for child care by an experienced baby sitter approved by the parent.

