8.2.2 Serious adverse events (SAEs)

A serious adverse event is any untoward medical occurrence or effect that

- results in death;
- is life threatening (at the time of the event);
- requires hospitalisation or prolongation of existing inpatients' hospitalisation;
- results in persistent or significant disability or incapacity;
- is a congenital anomaly or birth defect; or
- any other important medical event that did not result in any of the outcomes listed above due to medical or surgical intervention but could have been based upon appropriate judgement by the investigator.

An elective hospital admission will not be considered as a serious adverse event.

The investigator will report all SAEs to the sponsor without undue delay after obtaining knowledge of the events.

Version number: 5, 06-02-2018 30 of 46

The sponsor will report the SAEs through the web portal *ToetsingOnline* to the accredited METC that approved the protocol, within 7 days of first knowledge for SAEs that result in death or are life threatening followed by a period of maximum of 8 days to complete the initial preliminary report. All other SAEs will be reported within a period of maximum 15 days after the sponsor has first knowledge of the serious adverse events.

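### The adverse event rule in section 8.2.1 is written for the subject, meaning the father, although the ultrasound, massage and startle sound reach the partner, fetus and infant

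*Protocol*

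**What the plan says.** The definition in section 8.2.1 is "Adverse events are defined as any undesirable experience occurring to a subject during the study". The capture rule follows: "All adverse events reported spontaneously by the subject or observed by the investigator or his staff will be recorded". The clause on relatedness still carries a bracketed template list of alternatives from which nothing has been selected.

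Section 4.2 introduces eligibility with "In order to be eligible to participate in this study, a subject must meet all of the following criteria", and the first criterion is "Fathers having their first baby". The partner appears there only through conditions that her pregnancy must meet for the father to be eligible.

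On exposure, section 5.1 says of the intervention sessions: "Their partners are thus asked to cooperate and have the ultrasound made". It also has fathers touch and massage the fetus through the mother's abdomen. Section 7.3 describes an 80-db white noise played while the father plays with the baby at follow-up: "This sound is loud enough to elicit a response from the baby, without harming the infant's hearing".

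Section 8.2.2 defines a serious adverse event without naming whose event it is, includes congenital anomaly among the criteria, and makes one exception: "An elective hospital admission will not be considered as a serious adverse event".

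**The concern.** The physical exposures whose safety the protocol discusses in sections 10.4 and 12.2 include ultrasound and the startle sound. Ultrasound is applied to the mother and fetus, and the sound is heard by the infant as well as the father. A site that follows section 8.2.1 word for word would record a father's headache after the scanner. It would have no instruction to record, as an adverse event, a partner's complaint after a session or an infant's prolonged distress after the sound.

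The halt rule in section 8.1 is also keyed to the health or safety of subjects, so the same doubt about who is covered carries over to it. What is at stake is consistent recording and reporting to the ethics committee. The efficacy analyses are not affected.

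**Working it through.** No arithmetic decides this point. The check is to follow the words *subject*, *participant*, *partner* and *infant* through the protocol and compare them with who is exposed.

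**Who is the subject?**
- Section 4.1 recruits 140 fathers (2 x 70); partners and infants are not counted.
- Section 4.2 says "a subject must meet all of the following criteria", and the first criterion can be met only by a father.
- Section 7.3 names the partners of the participants as a separate group, and section 12.2 separates participants from their partners in the same way.
- Section 10.2 pulls the other way for the infant: both parents consent to the infant taking part. The partner also has her own consent form.

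**Who is exposed, and in which arm?**

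| Exposure | Person reached | Arm | Planned number, before attrition |
|---|---|---|---|
| Ultrasound, abdominal touch and massage (5.1, 6.6) | Partner and fetus | Intervention | up to 70 pregnancies |
| Startle sound (7.3) | Infant and father | Both; no restriction by arm is stated | up to 2 x 70 = 140 infants |

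**What does section 8 require for each person?**
- *Father:* all adverse events, reported by him or seen by staff.
- *Partner and fetus, non-serious events:* nothing is required on a literal reading. The staff-observation route widens who may notice an event. It does not widen whose event counts, because the definition has already limited adverse events to those occurring to a subject.
- *Infant, non-serious events:* arguably nothing. Section 4.2 leaves the infant out, while section 10.2 suggests the infant takes part.
- *Serious events in partner, fetus or infant:* unclear. If a serious event is read as a serious form of an adverse event, it inherits the limit to subjects. If section 8.2.2 is read on its own words, it has no such limit, and the congenital anomaly criterion most naturally concerns the child. The protocol does not say which reading applies, so the scopes of 8.2.1 and 8.2.2 do not match.

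**Does another section close the gap?**
- Section 7.1.3 collects the mother's reports on pregnancy, birth and the child's health, but as other study parameters, with no link to section 8.
- Section 12.2 refers fetal health issues seen during scanning to Document F21. That document is not shown, and the protocol does not tie it to adverse event recording.

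**The case against.** The strongest reply is that section 4.2 is an eligibility lead-in and not a definition, that usage elsewhere is mixed, and that the events that matter most are plausibly already reportable under 8.2.2. Much of this stands. It turns exclusion into ambiguity for serious fetal and infant events, and it weakens the case for the infant generally. It does not help with non-serious events in the partner and fetus, for whom no section widens the rule.

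A reader might infer several stronger things that the documents do not support:

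- *That the trial gathers no safety information on the exposed people.* It does gather some: section 7.1.3 collects pregnancy, birth and child-health data, an ultrasound professional carries out every scan, and Document F21 exists. What is missing is the route from these into adverse event recording.
- *That widening the term to the mother would make every non-elective hospital birth a serious adverse event, so that no reading is workable.* Section 8.2.2 first requires that the occurrence be untoward, and an uncomplicated delivery is not plainly that. The protocol gives no hospital-birth share, so the number of such admissions cannot be estimated. Because only elective admissions are excepted, the treatment of delivery admissions still deserves a sentence.
- *That the trial fails to support its own safety claim.* Zero events in 70 pregnancies would give a one-sided 95% upper bound of 1 - 0.05^(1/70) = 4.2%. That figure fits only the ultrasound arm, and the protocol does not propose to draw such an inference. It rests the safety of ultrasound on cited reviews and limits on scanning time.
- *That the unselected template bracket narrows the rule.* Events count whether or not they are considered related, so it does not; it is simply unfinished text.

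**Conclusion.** The point holds as a mismatch of scope. Section 8.2.1 defines adverse events only for the subject, a term that sections 4.1, 4.2 and 7.3 together attach to the father, while the intervention and one assessment act on other people. On a literal reading, non-serious events in the partner and fetus, and arguably the infant, fall outside adverse event recording. Serious fetal and infant events are ambiguous, and the reach of the halt rule in 8.1 is uncertain for the same reason.

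Its size is a count of people and not a bias or a loss of power: up to 70 pregnancies for ultrasound and massage and up to 140 infants for the sound, assuming the planned 2 x 70 and before attrition. The conclusion rests on the protocol text alone. It would soften if Document F21 contained an adverse event rule for the fetus, but nothing in the protocol says that it does. It is worth correcting because the correction is cheap.

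**What to change.** Reconcile sections 4.2, 8.1, 8.2.1, 8.2.2 and 10.2 as follows:

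1. State in section 8 that, for safety recording and reporting, events in the father, the pregnant partner, the fetus and the infant all count, in both arms, up to the home visit that section 11.5 takes as the end of the study. Apply the same scope to 8.1 and 8.2.2.
2. State how admissions for delivery are treated under the serious adverse event definition.
3. Complete the bracketed template text in 8.2.1 so that it names the intervention and the study assessments.
4. Name the pregnancy, birth and child-health reports already collected under 7.1.3 as a source for safety reporting, and say how Document F21 connects to it.

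The cost is protocol wording and some additional event records. No new procedure, visit or questionnaire is needed.

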8.2.2 Serious adverse events (SAEs)

A serious adverse event is any untoward medical occurrence or effect that

- results in death;
- is life threatening (at the time of the event);
- requires hospitalisation or prolongation of existing inpatients' hospitalisation;
- results in persistent or significant disability or incapacity;
- is a congenital anomaly or birth defect; or
- any other important medical event that did not result in any of the outcomes listed above due to medical or surgical intervention but could have been based upon appropriate judgement by the investigator.

An elective hospital admission will not be considered as a serious adverse event.

The investigator will report all SAEs to the sponsor without undue delay after obtaining knowledge of the events.

Version number: 5, 06-02-2018 30 of 46

The sponsor will report the SAEs through the web portal *ToetsingOnline* to the accredited METC that approved the protocol, within 7 days of first knowledge for SAEs that result in death or are life threatening followed by a period of maximum of 8 days to complete the initial preliminary report. All other SAEs will be reported within a period of maximum 15 days after the sponsor has first knowledge of the serious adverse events.

8.2.3 Suspected unexpected serious adverse reactions (SUSARs)

Not applicable

8.3 Annual safety report

Not applicable

8.4 Follow-up of adverse events

All AEs will be followed until they have abated, or until a stable situation has been reached. Depending on the event, follow up may require additional tests or medical procedures as indicated, and/or referral to the general physician or a medical specialist. SAEs need to be reported till end of study within the Netherlands, as defined in the protocol

8.5 [Data Safety Monitoring Board (DSMB) / Safety Committee]

Not applicable

Version number: 5, 06-02-2018

9. STATISTICAL ANALYSIS

9.1 Primary study parameter(s)

Hormonal

Effects of the VIPP-PRE intervention on hormonal responses to infant stimuli will be assessed using a General Linear Model (GLM) examining the between-group differences in within-subject (pre- and posttest) effects. Moreover, we will assess whether effects of VIPP-PRE on behavioral and neural outcomes are mediated by changes in basal hormonal levels.

Brain activity (fMRI)

Following preprocessing, both cluster corrected whole-brain, and region of interest analyses will be performed on a priori specified regions (see section 1.3), and psychophysiological-interaction (PPI) analysis will be used to examine functional connectivity among brain regions (e.g. amygdala – medial prefrontal cortex).

For the "processing infant signals" paradigms, contrasts comparing responses to infants' sounds and scrambled control sounds will be calculated and submitted to a GLM examining the between-group differences in within-subject (pre- and posttests) effects. Moreover, by examining sound x perception interaction analyses, we will assess whether the participants' perception of the cry sounds moderate their processing.

For the "processing threat to infant" video vignettes task, contrasts comparing responses to neutral and threatening videos, contrasts comparing child familiarity (own baby, unfamiliar baby) and their interactions will be calculated and submitted to a GLM examining the between-group (experimental and control group) differences in withinsubject (pre- and posttests) effects.

Behavioral

For the "handgrip during infancy stimuli" task, handgrip dynamometer force will be submitted to GLM with a 3 (time) x 2 (sound nature: infant stimuli versus scrambled sound) x 2 (child familiarity: own baby, unfamiliar baby) design. Group (experimental or control) will be modelled as a between subject factor.

Effects of the VIPP-PRE intervention on quantity of care (self-report, partner-report and ediaries) will be analyzed using a GLM examining the between-group (experimental and control group) differences in within-subject (pre- and posttests) effects.

32 of 46

Version number: 5, 06-02-2018

For the "quality of care" task and partner-report on quality of care, a GLM will be applied to assess the between-group (experimental and control group) differences in within-subject (pre- and posttests) effects.

For the "protection" task and protection questionnaire, a GLM examining the betweengroup differences in within-subject (pre- and posttest) effects.

If applicable, *p*-values will be corrected for multiple comparisons using a Bonferroni correction.

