4.4 Sample size calculation

The sample size will be 140 (N = 70 in each of the conditions), with 15% oversampling to compensate for attrition. On the basis of an expected meta-analytic effect size of r = .24 for the VIPP interventions (Juffer et al, 2010, 2017), power is $\geq .82$ (G*Power 3.1.9). This sample size provides also sufficient power to test indirect effects through hormone levels and neural processing, as the power of the test of indirect effects is (substantially) greater than the power of the test of direct effects (Kenny & Judd, 2014).

Version number: 5, 06-02-2018 19 of 46

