10.2 Recruitment and consent

A total of 140 fathers (2 x 70) will be recruited to take part in the study, with 15% oversampling to compensate for attrition. All recruitment and consent procedures listed below have recently been approved by the CCMO (document nr NL54702.058.15). Similarly to our pilot study (see NL54702.058.15), we will recruit through midwife agencies with the use of a recruitment letter (Document E3.1). Also, participants will be recruited using social media (e.g. Facebook), websites (e.g. the Leiden University website), and flyers (e.g. at pregnancy fairs, see Document E3.2), as was done in the pilot study (see NL54702.058.15). Eligible families will receive an invitation to participate in the study (Document E1.1). This invitation includes information about the study and a response card to express their interest for participation.

Interested fathers will receive a letter with detailed information about the study (Document E1.3) and will be informed that they will receive a phone call in a week. During this phone call, a research assistant will check the inclusion and exclusion criteria and answer questions. All interested fathers who reach us through other means (e.g. social media) will be sent an email with more information about the study (Document E1.2). Information collected from fathers who are excluded due to the outcome of the 20-week ultrasound will be deleted.

During all visits and sessions the fathers have the opportunity to ask questions before the intervention or measurement starts. Questions arising during the intervention or the lab visits will be answered as adequately as possible.

Written informed consent (IC) for participation, including fMRI measures, collection of saliva and hair, and the use of video/audio recordings collected during assessments (i.e. LISSA, sensitivity with own infant, and FMSS), will be obtained from the participant during the first lab visit (see Document E2.1 for the fathers' IC form). Both parents provide consent for participation of the infant, including the use of video recordings collected during assessments as well as the ultrasound images (see Document E2.1, and

Version number: 5, 06-02-2018

Document E2.2 for the partners' IC form). The consent forms will be stored in a locked filing cabinet accessible only to the investigators. At the time of consent, any remaining questions will be answered.

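### Most outcomes are tested as pre/post change without naming the pretest as a covariate: valid, but less powerful than a pretest-adjusted comparison, and not the test behind the stated power

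*Protocol*

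**What the plan says.** Section 9.1 uses nearly the same wording for hormones, both fMRI paradigms, quantity of care, quality of care and protection. The hormonal version reads "using a General Linear Model (GLM) examining the between-group differences in within-subject (pre- and posttest) effects". For handgrip, "handgrip dynamometer force will be submitted to GLM with a 3 (time) x 2 (sound nature: infant stimuli versus scrambled sound", with child familiarity as a further within-subject factor and group between subjects.

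Section 9.3 adds adjustment for pertinent covariates, with sports, food and drinks as examples. The pretest value of the outcome is not among those named.

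Section 4.4 bases the sample size on "an expected meta-analytic effect size of r = .24 for the VIPP interventions" and reports power of at least .82. On numbers it says "The sample size will be 140 (N = 70 in each of the conditions), with 15% oversampling to compensate for attrition", and section 10.2 repeats the 140 and the 15%.

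Section 7.6, headed "Follow-up of subjects withdrawn from treatment", is answered only as not applicable. Section 7.3 places the protection assessment in the follow-up session only.

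**The concern.** With two waves, a group difference in a within-subject effect is a two-sample t test on posttest minus pretest. Subtracting the pretest fixes its slope at 1. Using it as a covariate lets the data set the slope. When the pre-post correlation (rho) is modest, subtraction adds noise.

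The pretest is collected anyway, so precision is given up for nothing. The power in section 4.4 also belongs to a different test from the one in section 9.1, and a reader cannot tell from the protocol what power the planned test has.

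A smaller matter is section 7.6. Its answer leaves unclear whether a father who stops the intervention sessions but stays in the study is still invited to posttest and follow-up. Assessments that are not made cannot be recovered at the analysis stage.

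**Working it through.** **Inputs from the protocol.** r = .24, 70 per arm, power at least .82 (section 4.4); pre/post group-by-time GLM (section 9.1).

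**Assumptions.** Two-sided 5%; equal pre and post SDs; the effect expressed in posttest SD units; rho from .2 to .8. The protocol gives none of these.

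**Step 1: the stated power.** d = 2r/√(1 − r²) = 0.48/√(1 − 0.0576) = 0.494. A two-sample t test with 70 per arm has noncentrality d√(70/2) = 0.494 × 5.916 = 2.93 and power .828. A normal approximation gives .833 and the Fisher-z test of a correlation gives .817. The stated figure therefore reproduces as a two-group comparison at one time point with 140 analysed.

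**Step 2: the planned test.** In posttest SD units, change has variance 2(1 − rho), so its effective size is d/√(2(1 − rho)). The pretest-adjusted comparison (ANCOVA) has residual variance 1 − rho², so its effective size is d/√(1 − rho²). At rho = .3 these are 0.494/√1.4 = 0.418 and 0.494/√0.91 = 0.518. The variance ratio of change to adjusted is 2(1 − rho)/(1 − rho²) = 2/(1 + rho), which exceeds 1 for every rho below 1.

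**Step 3: power by noncentral t, 140 analysed.**

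| rho | change | pretest-adjusted | variance ratio |
|---|---|---|---|
| .2 | .632 | .842 | 1.67 |
| .3 | .690 | .861 | 1.54 |
| .4 | .755 | .887 | 1.43 |
| .5 | .828 | .918 | 1.33 |
| .6 | .901 | .953 | 1.25 |
| .7 | .963 | .982 | 1.18 |
| .8 | .996 | .998 | 1.11 |

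At rho = .5 the change variance factor is 2(1 − .5) = 1, so the change test has exactly the power of the simple comparison in step 1. Below .5 it has less and above .5 more. The adjusted comparison stays above .82 in every row.

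**Step 4: if 140 already includes the 15%.** Sections 4.4 and 10.2 do not settle this. With 140 × .85 = 119 analysed, change against adjusted is .62 against .80 (rho .3), .76 against .87 (.5) and .93 against .96 (.7).

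**Limits.** These figures are for two waves. The handgrip model has three times, so its group-by-time interaction is not a single change score and the table does not give its power. No Bonferroni correction is applied.

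**The case against.** The change contrast is unbiased under randomisation, so nothing here invalidates the planned tests. The gain depends on a correlation that the protocol does not give. At rho = .7 it is about 2 points of power, and the planned test then has .96, well above the stated .82. Section 9.3 also leaves room for covariates. All of this stands, and it limits the point to efficiency. It does not remove it: section 9.1 fixes a model, the pretest is not named, and the adjusted comparison is better at every rho below 1.

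A reader might infer more than the protocol supports.

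- *That the trial is underpowered.* This follows only if rho is below about .5, which the protocol neither states nor implies.
- *That only completers will be analysed.* A classical repeated-measures GLM drops fathers with a missing wave, but the protocol names no analysis set, missing-data rule or software. These are commonly left to the SAP, which is not at hand.
- *That fathers who stop sessions will not be assessed.* The entry in section 7.6 is a bare answer under a template heading, like many others in the document. It is ambiguous and is not a stated policy. Section 10.6 pays per lab visit, not per intervention session.
- *That dropout would favour the intervention by a calculable amount.* The bias of a change analysis depends on how far the change in fathers who are lost differs from the change in those who stay. A gap that is equal at pretest and posttest cancels. The protocol gives neither that difference nor dropout by arm. The direction is open as well: control fathers can decline their calls, and intervention fathers receive the ultrasound images only after completion.

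**Conclusion.** The point holds as one of efficiency, not validity. With 140 analysed, the planned two-wave test gives up about 17 points of power against a pretest-adjusted comparison at rho = .3, 9 points at .5 and 2 points at .7. This rests on equal SDs, two-sided 5% and d = 0.494 in posttest SD units. The stated power describes a simple two-group comparison and coincides with that of the planned test only at rho of about .5. No shortfall against .82 is established, and the protocol supports no bias or completers-only conclusion. Section 7.6 needs clarifying, as a secondary matter.

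**What to change.** In section 9.1, for outcomes with a pretest, replace the group-by-time GLM by a model of posttest and follow-up values on arm, visit and arm × visit, with the pretest value as covariate. Use ANCOVA where there is one post visit, and a mixed model with all available visits, as randomised, where there are two. For outcomes without a pretest, such as the observed protection task, specify a plain between-group comparison; the pre/post wording now attached to that task cannot be carried out.

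In section 4.4, say which test the power refers to and, if it is the adjusted one, which pre-post correlation is assumed.

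In section 7.6, replace the present answer with a statement that fathers who stop the sessions are still invited to posttest and follow-up unless they withdraw consent.

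The cost is a few sentences and possibly a few more assessments of fathers already enrolled. No extra recruitment is needed.
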